## **9 PHARMACOKINETICS AND PHARMACODYNAMICS**

This section is not applicable.

## **10 SAFETY ANALYSES**

### **10.1 Extent of exposure**

The duration of exposure of BRV (days) while in the study is calculated as:

Date of last administration of BRV while in the study – date of first BRV administration + 1.

For snapshot analyses, patients with missing date of last administration of BRV while in the study will be imputed using the date of data cut-off for the analysis. This assumes that patients still ongoing in the trial are still taking BRV.

All exposure analyses will be performed on the SS and the modified FAS.

Exposure will be summarized using descriptive statistics of the continuous variable duration of exposure (days). In addition, the following categories of duration of exposure (days) will show the number of patients with 1 day to <3 months BRV (1-<90 days), 3 months to <6 months BRV (90-<180 days), 6 months to <12 months BRV (180-<330 days), and ≥12 months BRV (≥330 days).

The number and percentage of patients receiving each daily BRV dose at Day 2, Day 7, Day 14, Day 21, Day 30, Day 60, Day 90, Day 120, Day 150, Day 180, Day 240 and Day 330 will be

summarized in the following BRV dose categories ( $\leq 10\text{mg}$ ,  $>10$  to  $<50\text{mg}$ ,  $\geq 50\text{mg}$  to  $<100\text{mg}$ ,  $\geq 100\text{mg}$  to  $<150\text{mg}$ ,  $\geq 150\text{mg}$  to  $\leq 200\text{mg}$  and  $>200\text{mg}$ ). In addition, the total number of patients receiving each Dose category at any time on the study will be presented. Day 1 will be equal to the first BRV administration date. Day 2 is considered as the starting dose due to some patients only receiving 1 dose (afternoon dose only) on Day 1.

Time to BRV maintenance dose will be summarized descriptively and will be defined as:

Date of first intake of the BRV dose the patient remained on for the longest time during the treatment period – Date of first BRV administration.

If there is more than one dose which was taken for the equally longest time during the treatment period then the date of the first intake of the latter BRV dose will be used in the above calculation. If the patient has the same BRV dose twice (or more than twice) with a gap of BRV treatment in-between then the durations will not be added together to identify the BRV dose the patient remained on for the longest time; they will be considered separately. Similarly if the patient has the same BRV dose at least twice with another BRV dose in-between then the durations will not be added together; they will be considered separately.

A by-patient listing of exposure to BRV while in the study (including the start and stop dates of BRV, duration of exposure, and exposure category) will be provided on the All Subjects Documented set.

## 10.2 Adverse events

Adverse events and other safety relevant (OSR) information such as overdose or off label use, will be recorded using UCBs Pharmacovigilance database.

The UCB SafetyAdHoc Team will provide an ad hoc listing of the safety data with an additional variable named “Case Classification (All)” that allows identification of the “non-reportable” events. Only events that are identified as “reportable” (ie, where Case Classification (All) variable does not include “Non-Reportable”) will be imported into the clinical database (SDTM). A list of MedDRA preferred terms (PTs) will be reviewed prior to database lock and used to identify OSR information. All PTs will be classified as AEs or OSR information. OSR information will not be included in the AE tables and listings, with the exception of the overview table for treatment-emergent adverse events (TEAE, see definition below) and OSR information, and the listing of AEs and OSR information that could not be reconciled.

A treatment-emergent adverse event (TEAE) is defined as an AE occurring on or after the date of first BRV administration.

An ADR is defined as a TEAE with an “as reported causality” as “related”, “unavailable” or missing.

In order to investigate the time to discontinuation of BRV due to ADRs, the time to discontinuation of BRV for all patients, will be calculated as:

Date of last administration of BRV while in the study – date of first BRV administration + 1

The date of last administration of BRV while in the study (both for completers and dropouts) and the date of first BRV administration will be taken from the CRF Study Termination (Completed Subject), Study Termination (Dropout), and First Administration of Drug pages. All patients who have an ADR with action=“Drug withdrawn” (recorded in the UCBs Pharmacovigilance

database) will be classed as having an event (discontinued BRV due to an ADR). All other patients will be censored. Time to discontinuation of BRV due to ADRs will be analyzed on the SS using Kaplan-Meier methods. The median time to discontinuation (days) of BRV due to ADRs (and 95% CI) will be presented along with the 25% and 75% quartiles (and 95% CI for the quartiles). The Kaplan-Meier plot and raw statistical procedure output will also be produced for the Kaplan-Meier analysis.

For each of the following event types, frequency tables of incidence based on the SS will be presented. The overview analysis of TEAEs and ADRs will also be repeated on the modified FAS:

- Overview of TEAEs and OSR information (including categories for any TEAE, serious TEAE, patient discontinuations of BRV due to TEAE [derived as any TEAEs with action= “Drug withdrawn”], drug-related TEAE [ADRs], all deaths [AEs leading to death], and OSR information
- Overview of ADRs (including categories for any ADR, serious ADR, patient discontinuations of BRV due to ADRs [derived as any ADRs with action= “Drug withdrawn”], and all deaths [ADRs leading to death])
- TEAEs by MedDRA SOC and PT
- ADRs by MedDRA SOC and PT
- Non-serious TEAEs above reporting threshold of 5% of patients by MedDRA SOC and PT
- Non-serious ADRs above reporting threshold of 5% of patients by MedDRA SOC and PT
- TEAEs occurring in at least 5% of patients by MedDRA SOC and PT
- ADRs occurring in at least 5% of patients by MedDRA SOC and PT
- Serious TEAEs by MedDRA SOC and PT
- Serious ADRs by MedDRA SOC and PT
- Serious TEAEs – patient numbers
- Serious ADRs – patient numbers
- ADRs leading to permanent discontinuation of BRV by MedDRA SOC and PT
- TEAEs leading to death by MedDRA SOC and PT
- ADRs leading to death by MedDRA SOC and PT
- TEAEs by maximum relationship by SOC and PT

An AE Glossary (including the SOC, PT and reported term) will be provided separately for AEs and OSR information. In addition, the following by-patient listings for the All Subjects Documented set will be presented including the MedDRA SOC and PT, reported term, onset and outcome date, duration, seriousness, death, congenital defect, disability, hospitalization, life threatening, medically important event, outcome, relationship to study medication, and action taken with regards to study medication:

- All AEs (this listing will be repeated for patients aged <18 years only)

- All serious AEs
- All AEs leading to permanent discontinuation of BRV
- All deaths (AEs leading to death)
- OSR information
- AEs and OSR information that could not be reconciled (ie, AEs/OSR information for patient numbers that do not exist in the clinical database). This would be an ad hoc listing which will not be produced until after database lock if necessary.

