#### 10.1.2 Other safety relevant information

Other safety relevant information includes the following:

- Off-label use

This relates to situations where BRV is intentionally used for a medical purpose not in accordance with the authorized product information.

- **Misuse**  
This refers to situations where BRV is intentionally and inappropriately used not in accordance with the authorized product information.
- **Abuse**  
This corresponds to the persistent or sporadic, intentional excessive use of BRV, which is accompanied by harmful physical or psychological effects (2010/84/EU Art 1).
- **Medication error**  
For the purpose of this NIS, medication error refers to any unintentional error in the prescribing, dispensing, or administration of BRV while in the control of the healthcare professional, patient, or consumer.
- **Occupational exposure**  
This refers to the exposure to BRV (as defined in 2010/84/EU Art 1), as a result of one's professional or nonprofessional occupation.
- **Lack of therapeutic effect**
- **Overdose**  
See [Section 10.1.6](#).
- **Suspected transmission of an infectious agent via BRV**
- **Suspected adverse reaction associated with a suspected or confirmed falsified medicinal product or quality defect (combined complaint) of BRV**
- **Unexpected therapeutic effect**

Note: Reports of off-label use, misuse, abuse, medication error, occupational exposure, lack of drug effect, overdose, transmission of infectious agent, falsified medication, or unexpected therapeutic effect should be reported as described in [Section 10.1.8](#) if considered medically important events by the treating physician.

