### **10.1.3 Reporting and description of AEs or other safety relevant information**

In order to ensure complete safety data collection, all AEs and other safety relevant information occurring during the study (ie, after signing the Patient Data Consent form), must be reported. This includes all AEs not present prior to the initial visit and all AEs that recurred or worsened after the initial visit (eg, underlying or previous concomitant disease).

Signs or symptoms of the condition/disease for which the prescribed treatment is being studied should be recorded as AEs only if their nature changes considerably or their frequency or intensity increases in a clinically significant manner as compared to the clinical profile known to the treating physician from the patient's history or the Baseline Period.

When recording an AE, the treating physician should use the overall diagnosis or syndrome using standard medical terminology, rather than recording individual symptoms, signs, or medical procedures. The Adverse Event Report form for NIS and source documents should be consistent.

Details for completion of the Adverse Event Report form for NIS are described in the AE reporting instructions.

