#### **10.1.6 Overdose of prescribed treatment**

Overdose of prescribed treatment refers to the administration of a quantity of a medicinal product given per administration or cumulatively which is above the maximum recommended dose according to the authorized product information.

Overdose should be reported on the Adverse Event Report form for NIS, independently of whether there is an AE associated with the excessive dosing or not.

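### A serious or fatal event coded only to an 'other safety relevant' (OSR) preferred term is absent from the SAP's serious-event and death counts

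*SAP*

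**What the plan says.** SAP Section 10.2 first separates two kinds of record held in the sponsor's pharmacovigilance database. The separation works on the coded term: "A list of MedDRA preferred terms (PTs) will be reviewed prior to database lock and used to identify OSR information", and "All PTs will be classified as AEs or OSR information". No other criterion is given. Overdose and off-label use are the two examples of OSR information that the SAP names.

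The section then restricts where OSR information may appear: "OSR information will not be included in the AE tables and listings, with the exception of the overview table". The exception continues: it covers the overview of TEAEs and OSR information, and also the listing of records that could not be reconciled with the clinical database. A dedicated by-patient OSR listing is planned as well, with the same fields as the AE listings, including seriousness, death, hospitalization, relationship and action taken.

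The definitions are nested. A TEAE is an AE with onset on or after first brivaracetam (BRV) administration. An ADR is a TEAE whose reported causality is related, unavailable or missing. The death row of the overview is worded "all deaths [AEs leading to death" and the death listing is defined in the same way. The serious and fatal tables are built on TEAEs and ADRs.

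On the protocol side, Section 10.1.2 lists overdose, abuse and lack of therapeutic effect among the OSR items, and describes abuse as use "which is accompanied by harmful physical or psychological effects". Section 10.1.6 says "Overdose should be reported on the Adverse Event Report form for NIS", whether or not an AE accompanies it. Section 10.1.3 asks physicians to record an AE as an overall diagnosis or syndrome "rather than recording individual symptoms, signs, or medical procedures".

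**The concern.** Whether a record is OSR depends only on its term, but an OSR record can describe harm. The SAP allows for this itself, since its OSR listing carries seriousness, death and hospitalization fields. If a fatal or serious overdose reaches the database under that one term, the rule keeps it out of every count that a reader would consult for serious or fatal outcomes.

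Incidence of serious treatment-emergent AEs and ADRs is a listed variable (Protocol 4.4, SAP 2.2.4), and a row labelled as all deaths will be taken to mean all deaths. The single OSR row in the overview shows that a patient had such a record, but not that it was serious or fatal. These outcomes are rare, so one misplaced record can be the whole result. The protocol's AE definition (10.1.1) contains no exclusion by coded term, and SAP 3.9, which lists changes to protocol-defined analyses, does not mention one.

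**Working it through.** The plan gives no figure for OSR events, so there is nothing to reproduce. The check has two parts.

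**1. Applying the rule.** Inputs, all from SAP 10.2: term class (AE or OSR); a TEAE requires class AE; an ADR requires a TEAE with causality related, unavailable or missing; serious and fatal tables use TEAEs or ADRs; the death row and listing use AEs. Four hypothetical patients, all with onset after first BRV and causality recorded as related:

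| Records in the database | Serious TEAE / ADR | Death row | OSR row |
|---|---|---|---|
| A. Overdose term only, fatal | no | no | yes |
| B. Overdose term plus a clinical AE term, the AE serious and fatal | yes | yes | yes |
| C. Abuse term only (if classed OSR), serious, not fatal | no | not applicable | yes |
| D. Clinical AE term only, fatal | yes | yes | no |

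Patients A and B may have had the same clinical course. They differ only in whether a second term was coded. Nothing in SAP 10.2 returns A or C to the serious or fatal counts.

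**2. Size, as an illustration.** AE tables use the Safety Set. Its size is not stated; 530 (the planned enrolment in SAP 2.3) is assumed, with 385 (the Full Analysis Set target in SAP 2.4) as a smaller comparison. The number of serious or fatal OSR-only patients is also unknown; 1 to 5 is assumed. The intervals are two-sided exact (Clopper-Pearson), the method SAP 8.1.1 uses for retention. The SAP plans no interval for AE incidence, so they serve only to show scale.

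For 0 events the upper limit is 1 − 0.025^(1/N):

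- N = 530: 1 − 0.025^(1/530) = 0.69%
- N = 385: 1 − 0.025^(1/385) = 0.95%

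For x > 0 events the lower limit is the 2.5% point of Beta(x, N − x + 1) and the upper limit is the 97.5% point of Beta(x + 1, N − x):

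| True events | N = 530 | N = 385 |
|---|---|---|
| 0 (as tabulated if all are omitted) | 0% (0 to 0.69%) | 0% (0 to 0.95%) |
| 1 | 0.19% (0.00 to 1.05%) | 0.26% (0.01 to 1.44%) |
| 5 | 0.94% (0.31 to 2.19%) | 1.30% (0.42 to 3.00%) |

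One omitted patient moves the rate by 1/530 = 0.19 percentage points. That is small, but it turns one event into none.

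**The case against.** Several points on the other side are sound and limit the concern.

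- **The records are not lost.** A reader might infer that OSR records vanish from all AE output. They do not: the exception reads "with the exception of the overview table for treatment-emergent adverse events (TEAE, see definition below) and OSR information", and the OSR listing shows seriousness, death and action taken for each record. Disposition tables (SAP 5.1) count dropouts and BRV discontinuations from the CRF whatever the term class. The gap is in the summary counts and their labels.
- **The omission is conditional.** A reader might infer that any serious overdose or abuse event is missed. Patient B shows otherwise. Protocol 10.1.6 treats the overdose and any associated AE as separate things, and 10.1.3 requires all AEs to be reported. The advice to record one overall diagnosis makes a single-term report possible; it does not show that such reports occur.
- **The term list is not in the documents.** Overdose is named as OSR in the SAP. Abuse is an OSR item only in the protocol, so its class in the analysis is likely but not stated.
- **Discontinuation counts are a different matter.** A reader might infer that OSR records with the action 'Drug withdrawn' should also become TEAEs or ADRs. The documents speak against that. Lack of therapeutic effect is an OSR item (Protocol 10.1.2), and withdrawals for lack of effectiveness must be reported (Protocol 8.2). If such terms are classed as OSR, efficacy withdrawals would become discontinuation TEAEs and, where causality is related, unavailable or missing, ADR events in the Kaplan-Meier analysis. For scale: at the planning retention of 50%, 0.5 × 530 = 265 patients are not retained; if 20% to 50% of them stopped for lack of efficacy (assumed), 53 to 133 patients, or 10% to 25% of 530, could be affected. Keeping OSR out of the discontinuation counts is defensible.

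What none of this answers is patient A: a fatal overdose coded to that term alone is in no death count.

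**Conclusion.** The point holds in a limited form. Under SAP 10.2 as written, a serious or fatal event coded only to an OSR term is absent from the serious TEAE, serious ADR and fatal-event tables and from the row and listing presented as all deaths. It appears only as an unspecified entry in the OSR row and in the OSR listing. This follows from the definitions and needs no assumption about data.

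How much it matters in practice does rest on assumptions: that a harmful OSR event is coded without a separate clinical AE term, and that its term is on the unseen OSR list. The frequency is unknown and may be zero. If there were one such patient in a Safety Set of 530, the tables would show 0% (0 to 0.69%) where the complete figure is 0.19% (0.00 to 1.05%). The documents do not support a claim that serious overdose or abuse events are generally missed, or that the discontinuation counts are wrong.

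**What to change.** Amend SAP 10.2 before database lock, when the term list is due for review anyway:

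1. Define all deaths, in both the overview row and the listing, by fatal outcome of any reportable record, whether its term is classed AE or OSR.
2. Split the OSR row of the overview into any, serious and fatal.
3. Beside the serious TEAE and serious ADR counts, show the number of patients whose only serious or fatal record on or after first BRV administration carries an OSR term, and state that these patients are not in the TEAE or ADR counts.

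Do not reclassify OSR records as TEAEs or ADRs merely because the action taken is 'Drug withdrawn', for the reason given under the objection. If that information is wanted, add it as a further display row within OSR.

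The cost is a short paragraph and a few table rows, using fields already planned for the OSR listing. Reported serious or fatal numbers can stay the same or rise slightly.

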## 8.2 Withdrawal criteria

Patients are free to withdraw from the NIS at any time, without prejudice to their continued care.

Physicians are free to add or withdraw any medication or to withdraw the patient from the study at their own discretion.

If the physician elects to permanently stop BRV treatment, the patient will be withdrawn from the study.

The primary reason for withdrawal from the NIS must be documented in the patient's eCRF. When the primary reason for withdrawal is lack of effectiveness or an AE, both must be reported as described in [Section 10.1.8](#) of the protocol.

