### **10.1.8 Procedures for reporting AEs or other safety relevant information**

The patient will be given the opportunity to report AEs spontaneously. A general prompt will also be given at each study visit to detect AEs, for example:

“Did you notice anything unusual about your health (since your last visit)?”

In addition, the treating physician should review any self-assessment procedures (eg, epilepsy/seizure diary, questionnaires) employed.

If an AE or other safety relevant information is reported, UCB must be informed within 1 working day of receipt of this information by the site (see contact information for AE reporting listed in the contact information for AE transmission of the NIS protocol). The treating physician must forward to UCB (or its representative) a duly completed Adverse Event Report form for NIS provided by UCB, even if the data are incomplete or if it is obvious that more data will be needed in order to draw any conclusions. Information recorded on this form will be entered into the global safety database.

If clarifications on the AE or other safety relevant information are necessary, UCB shall request additional information from the treating physician.

The Adverse Event Report form for NIS and other requested information must be provided in English.

Additional information (eg, autopsy or laboratory reports) received by the treating physician must be provided within 1 working day.

All documents in the local language must be accompanied by a translation in English, or the relevant information included in the same document must be summarized in the Adverse Event Report form for NIS.

The treating physician is specifically requested to collect and report to UCB (or its representative) any AEs or other safety relevant information, and to also inform participating patients of the need to inform the treating physician of any AE or other safety relevant information during the study.

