## 5 STUDY POPULATION CHARACTERISTICS

### 5.1 Subject disposition

The following tables will be produced on the All Subjects Documented set:

- Disposition of All Subjects Documented. For all study sites and by study site, this table will show the date of the first patient in/last patient out and the number of patients in the All Subjects Documented set, FAS, SS and modified FAS.
- Disposition of Analysis sets to include the number and percentage of patients in the All Subjects Documented set, FAS, SS and modified FAS
- Disposition and Discontinuation Reasons including:
  - Number and percentage of patients completing or prematurely discontinuing the study with discontinuation reason (as recorded in the Study Termination NIS (Dropout) and Study Termination NIS (Completed Subject) CRF pages)
  - Number and percentage of patients continuing or discontinuing BRV after study participation in this NIS with discontinuation reason (as recorded in the Post-Study Treatment Continuation and Medication Discontinuation CRF pages)
- Number and percentage of patients attending each scheduled visit (including mapping of withdrawal visits as described in [Section 3.2.2](#))

In addition to a study eligibility criteria text listing, the following by-patient listings on the All Subjects Documented set will be produced:

- Patients who did not meet study eligibility criteria
- Patient disposition (including first and last BRV dose, completion and early discontinuation information, primary reason for discontinuation, whether the patient is prescribed BRV after exiting the study and the main reason for BRV discontinuation)
- Patient discontinuation (only including patients who discontinue)
- Patient analysis sets
- Patients excluded from analysis sets with reason for exclusion
- Visit dates

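### Discontinuation of BRV due to an ADR rests solely on the safety-database action field, so the rule can count a patient who completes on BRV and miss one whose CRF records a stop for an AE

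*SAP*

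**What the plan says.** Protocol 4.4 lists four tolerability and safety variables. Two of them concern ADR discontinuation: the time to it, and the incidence of ADRs leading to it.

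For the time variable, SAP 10.2 classes as events "All patients who have an ADR with action=“Drug withdrawn” (recorded in the UCBs Pharmacovigilance" database, and then states "All other patients will be censored". The overview table of ADRs uses the same field: "patient discontinuations of BRV due to ADRs [derived as any ADRs with action= “Drug withdrawn". The SOC/PT table of ADRs leading to permanent discontinuation is listed without a derivation of its own.

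Causality comes from the same database and has an explicit missing-data rule: "An ADR is defined as a TEAE with an “as reported causality” as “related”, “unavailable” or missing". No such rule is given for a missing action, and SAP 4.2 excludes imputation outside its listed exceptions, none of which covers this field.

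The time to event comes from the CRF. "The date of last administration of BRV while in the study (both for completers and dropouts") is used together with the first-dose date, so completers can enter as events.

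The CRF also holds the reason for stopping. Protocol 8.2 says "The primary reason for withdrawal from the NIS must be documented" in the eCRF, and Protocol Table 17-1 schedules the reason for stopping BRV at Visit 4 or the Withdrawal Visit. SAP 5.1 tabulates reasons for stopping BRV "as recorded in the Post-Study Treatment Continuation and Medication Discontinuation CRF pages". SAP 10.2 does not use them.

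**The concern.** A single field decides the event, and the rule contains no check against the CRF in either direction.

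First, it does not require that BRV ended. SAP 10.2 does not define *Drug withdrawn* as permanent. A patient with that action who restarts BRV and finishes the study on it becomes an ADR discontinuation, timed at the last in-study dose and not at the interruption.

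Second, a missing or outdated action is treated as no discontinuation. Protocol 10.1.8 has safety forms sent within 1 working day, "even if the data are incomplete or if it is obvious that more data will be needed", and at that point the action taken may not be known. Missing causality counts towards an ADR, while a missing action counts against a discontinuation. The two gaps are handled in opposite ways within one definition.

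At stake is whether the ADR discontinuations reported are a proper subset of the discontinuations reported elsewhere in the same study report.

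**Working it through.** **1. No plan figure to reproduce.** The documents state no expected rate, event count or precision for ADR discontinuation.

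**2. The rules side by side for two possible patients.** Patient A has an ADR with action *Drug withdrawn*, restarts BRV, completes the study at least 330 days after first dose, and will be prescribed BRV after exit. Patient B stops BRV before that point, has a Dropout page with AE as the CRF reason, and has a related ADR with the action field blank.

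| Rule | Patient A | Patient B |
|---|---|---|
| SAP 5.1 disposition | Completer, continuing BRV | Discontinued, reason AE |
| SAP 8.1.1 retention | Retained | Not retained |
| SAP 8.1.2 Kaplan-Meier | Censored | Event |
| SAP 10.2 Kaplan-Meier | Event | Censored |
| SAP 10.2 ADR overview | Counted | Not counted |

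Retention for A requires last dose minus first dose ≥ 330 days. The SAP 10.2 time is that difference plus 1, so A's event falls at Day 331 or later. In both columns, SAP 10.2 gives the opposite status to SAP 8.1.2.

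**3. Size of a lost-event error in the count (assumed inputs).** Take 530 patients (planned enrolment; the Safety Set may be smaller) and assume a true ADR-discontinuation rate of 10%.

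- True events: 530 × 0.10 = 53.
- Action missing in 10%: 53 × 0.10 = 5.3 lost; (53 − 5.3)/530 = 9.0%.
- Action missing in 30%: 53 × 0.30 = 15.9 lost; (53 − 15.9)/530 = 7.0%.
- For scale, the 95% half-width at 10% is 1.96 × √(0.10 × 0.90/530) = 2.6 percentage points.

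**4. Effect on the Kaplan-Meier curve (simulation, assumed inputs).** There were 100 runs with N = 530: true ADR discontinuation 5%, 10% or 15%; other discontinuation 25%, spread evenly to Day 329; ADR stops exponential with mean 80 days, capped at Day 329; completers' last dose between Day 330 and Day 420. Entries are mean cumulative incidence. True values slightly exceed the crude rates because other stops are censored.

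| Scenario | 5% | 10% | 15% |
|---|---|---|---|
| True, Day 329 and end of curve | 5.4% | 10.7% | 16.0% |
| Action captured in 90%, Day 329 | 4.8% | 9.7% | 14.6% |
| Action captured in 80%, Day 329 | 4.3% | 8.6% | 13.0% |
| Action captured in 70%, Day 329 | 3.8% | 7.6% | 11.5% |
| 1% of completers counted wrongly, end of curve | 10.3% | 16.3% | 21.4% |
| 3% of completers counted wrongly, end of curve | 19.1% | 24.6% | 29.0% |

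Wrongly counted completers leave Day 329 unchanged. They fall where few patients remain at risk, so each one moves the curve a long way. SAP 10.2 reports quartiles, and the 25% quartile exists only if cumulative incidence reaches 25%. At a true 16.0%, 3% wrongly counted completers take the mean end-of-curve value to 29.0%, so a quartile could be printed that should not exist.

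The errors can offset in the count and still distort the curve. With 80% capture and 2% of completers wrongly counted, at the 10% rate, 49.1 events are counted against 53.0 true. Day 329 is then 8.6% and the end of the curve 19.0%, both against 10.7%.

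**The case against.** The choice of source is reasonable. Causality and action are held per event in the safety database, and a patient-level CRF reason cannot by itself fill an SOC/PT table. The CRF is not ignored altogether, since it supplies the dates. This stands, and the fix keeps the safety database as the main source.

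The risk of lost events is reduced by text in the protocol. Section 8.2 requires an AE that causes withdrawal to be reported to safety. Section 10.1.8 has the sponsor request clarification, and has additional information forwarded within 1 working day. Section 10.1.4 requires follow-up, and 13.2.2 provides for discrepancy checks. By-patient listings of stop reasons and of action taken would allow a manual comparison. This also stands. But none of it guarantees a completed action field at lock or says which source prevails, and the only reconciliation named in SAP 10.2 concerns patient numbers absent from the clinical database.

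Including completers appears deliberate. The change log for SAP Amendment 3 shows that a dropout condition was removed, and a completer who stops BRV at exit because of an ADR is a genuine event. That argues for keeping such completers. It does not argue for keeping those who continue BRV, whom the CRF question on prescription after exit identifies. Protocol 8.2 withdraws a patient whose physician permanently stops BRV, so a completer with this action is either a stop at exit or not a permanent stop.

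A reader might infer that any difference from the disposition table proves an error. It does not: disposition gives one primary reason whatever the causality, so an unrelated AE, or an ADR that contributed without being the primary reason, should differ. Nor do the documents say that temporary interruptions are coded *Drug withdrawn*.

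**Conclusion.** The point holds as a gap in the definition. As written, SAP 10.2 can make an ADR-discontinuation event of a patient whom SAP 8.1.1 counts as retained and SAP 8.1.2 censors. It can also censor a patient whose CRF records a stop for an AE with a qualifying ADR.

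It would go too far to say that the reported rates are wrong in both directions, or that undercounting will occur. The frequency of missing actions, and of completers carrying the action, is not in the documents. The losses of 1 to 3 percentage points at a 10% rate, and the simulated curves, rest wholly on assumed inputs; the count loss is of the same order as the sampling error of 2.6 points.

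A reader might also infer that the main result is at risk. It is not: primary retention uses CRF dates and does not depend on this field, and both documents present retention as a measure of effectiveness. The affected variables are descriptive. The change is still worth making before lock, because it is cheap and makes ADR discontinuation a subset of discontinuation.

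**What to change.** Define an ADR-discontinuation event as a patient who meets both conditions:

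1. the SAP 8.1.2 discontinuation definition: Dropout page completed, or *No* to BRV being prescribed after study exit; and
2. either an ADR with action *Drug withdrawn*, or a CRF primary reason for stopping BRV of AE together with an ADR whose action is missing or unknown.

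The SAP 3.2.4 last-dose date should not serve as proof of stopping, because it is defined for completers who continue BRV as well.

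Before database lock, compare the CRF stop reason with the safety-database action for every patient and query mismatches. Confirm by query which ADR is concerned, so that it can be placed in the SOC/PT table. The comparison is also needed for a patient whose BRV was interrupted for an ADR and who later drops out for another reason, since the flag alone would still count that patient.

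Use the same flag in the Kaplan-Meier analysis, the ADR overview and the SOC/PT table of ADRs leading to permanent discontinuation. Show the action-field-only result as a sensitivity analysis.

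Cost: SAP wording, one cross-source check on data already collected, some extra queries, and possibly a slightly less favourable ADR-discontinuation rate.
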